Global tolerability assessment by blinded study staff and patient						•
Local tolerability assessment (subjective symptoms: burning, paraesthesia, pruritus) by the patient ^D		•	•	•	•	•
Skin irritation assessment: secondary infection, erythema, excoriation by blinded study staff ^D		•	•	•	•	•
Hair scalp assessment for living lice (all stages) by blinded study staff				•	•	•
Eyes irritation assessment by blinded study staff ^D		•	•	•	•	•
Questioning on general well- being by blinded study staff		•	•	•	•	•

Procedure Screening Visit V01					Second Treatment Visit V03	Follow-up Visit V04	
Study day	Day 0			Day 1 (±3h)	Day 7 (+1d)	Day 10 (-1d; +2d	
	-2h	0h	+1h	24h after end of administration (±3h)			
Questioning on AE by blinded study staff	•		•	•	•		
Questioning on patient's combing		•	•	•			
Check of restrictions				•	•	•	
Questioning on satisfaction with the esthetical effect ^E	•			•			
Discharge from clinical study						•	

^A Pregnancy tests (urine) will be performed in all female patients with childbearing potential prior to study start

^B Baseline assessments within 1h prior to administration on day 0 and day 7, on day 7 the pre-treatment assessment for irritations (skin, eyes) have to be used for decision about withdrawal due to severe irritation

^C The time of exposure to the investigational products on the uncovered hair will not exceed 10 + 2 minutes for the test product and 30 – 45 + 5 minutes for the reference product GOLDGEIST[®] FORTE

^D Assessments after administration will be performed directly after start of the treatment plus 5 minutes as well as after the end of administration (the contact time is over and the investigational product is rinsed) within 15 minutes.

^E Satisfaction with the esthetical effect will be performed on day 0 and day 7 after treatment and hair drying by the patients

For all other assessments a deviation up to ± 20 min from scheduled time will be accepted.

4 Signature pages

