15.5 Assessments

Assessments for skin irritation and eyes irritation directly prior to administration (baseline as well as assessments on day 7) will be performed within 1 hour before administration.

Assessments for local tolerability, global tolerability, skin irritation and eyes irritation after administration will be performed directly after start of the treatment plus 5 minutes as well as after the end of administration (the contact time is over and the investigational product is rinsed) within 15 minutes.

For all other assessments a deviation up to ± 20 min from scheduled time will be accepted.

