15.5.3 Skin irritation assessment

Skin irritation (secondary infection, erythema, excoriation) will be assessed by blinded and trained study staff within 1 hours before first treatment (baseline), as well as directly after study drug application and after the end of treatment on study day 0, day 1, day 7 (pre-treatment, 0h and 1h p.a.) and on day 10.

For the assessment of skin irritation the following 4-category scale as mentioned above will be used.

Score 1 = no

Score 2 = mild

Score 3 = moderate

Score 4 = severe

It will be investigated, whether the investigational products may cause symptoms of skin irritation.

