15.5.4 Eyes irritation assessment

To investigate a potential irritation of the eyes due to the treatment, the trained and blinded study staff will be assessed the severity of redness on both eyes (left, right) within 1 hours before first treatment (baseline), as well as directly after study drug application and after the end of treatment on study day 0, day 1, day 7 (pre-treatment, 0h and 1h p.a.) and on day 10.

For the assessment of eyes the following 4-category scale as mentioned above will be used.

Score 1 = no

Score 2 = mild

Score 3 = moderate

Score 4 = severe

It will be investigated, whether the investigational products may irritate the eyes.

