16.2 Description

Descriptive statistics of all endpoint variables will be tabulated (continuously scaled variables: mean, standard deviation, median, min, max, categorically scaled variables: counts and percentages) by visit and treatment.

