16.8 Quality control for statistical procedures

The statistical analysis will be conducted in compliance with the ICH E9 Note for Guidance on Statistical Principles for Clinical Trials (CPMP/ICH/363/96, 1998).

Quality control will be performed according to the SOPs of ACOMED statistik. Quality control includes checks of data, checks of calculations as well as formal checks of tables, listings and figures. All steps of quality control will be documented with signature of the reviewer and date of review.

17 Evaluation of efficacy parameters

The ITT population will be used for analysis of efficacy variables with exception of noninferiority, where PP population will be investigated.

The primary analysis will be repeated for PP population.

Missing values will not be imputed patients dropping out because of non-effective treatment will be counted as non-responders by study design.

Details of the analysis will be fixed in the Statistical Analysis Plan (SAP) which will be finalised before database lock.

18 Evaluation of safety parameter

For definition of safety set/population see section 16.1.

All analyses will be performed for the safety population. Due to the short treatment duration, the topical administration (associated with a low risk of systemic availability of pyrethrum or mineral oil) and comprehensive data on the safety profile of the active substance, laboratory safety tests will not be performed routinely.

Secondary parameters for tolerability and safety:

Local tolerability assessment (subjective	Burning, paraesthesia, pruritus at day 0 (0h, 1h), day 1, day 7 (0h, 1h) and day 10 p.a.
symptoms)	Frequencies and percentages (related to number of patients with information) will be given for each symptom.
Global tolerability	Patients will assess the overall treatment tolerability at day 10 p.a.
assessment (patient):	Frequencies and percentages (related to number of patients with

	information) will be given for each score as well as for the combined score "very good" / "good".
Global tolerability assessment (study staff):	The investigator will assess the overall treatment tolerability at day 10 p.a.
	Frequencies and percentages (related to number of patients with information) will be given for each score as well as for the combined score "very good" / "good".
Skin irritation	Secondary infection, erythema, excoriation of the skin at -1h (baseline assessment), day 0 (0h, 1h), day 1, day 7 (pre-treatment, 0h, 1h) and day 10 p.a.

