	Frequencies and percentages (related to number of patients with information) will be given for each symptom
Eyes irritation	Irritation/Redness of the eyes at -1h (baseline assessment), day 0 (0h, 1h), day 1, day 7 (pre-treatment, 0h, 1h) and day 10 p.a.
	Frequencies and percentages (related to number of patients with information) will be given for each symptom.
PTSS, Adverse Events:	Pre-treatment signs and symptoms and treatment emergent adverse events will be described by frequencies on WHO preferred term and system organ class level.

19 Evaluation patient reported outcomes

Secondary parameters:

Satisfaction with the	The patient will assess the satisfaction with the esthetical effects of
esthetical effect:	the anti-lice product after treatment and hair drying on day 0 and day 7 p.a.

Frequencies and percentages will be given for each question.

20 Quality assurance

Quality assurance includes all activities undertaken during and after a clinical study to verify and control quality. It embraces internal quality control by the staff itself and by independent second persons as well as monitoring and separate auditing activities. All activities will be performed according to written procedures of the CROs and the facilities involved.

At CardioSec all processes of planning, performance and evaluation are embedded in a comprehensive quality assurance system.

Monitoring of the study will be performed in accordance with the requirements of ICH-GCP.

The monitor is responsible for review of the written Informed Consent, for documentation of ethics committee and ministry of health approvals, for routine review of the CRFs throughout the study, for verifying adherence to the protocol, amendments, study specific SOPs and the completeness, consistency and accuracy of the data being entered on them. All demographic and safety parameters will be 100% verified by the monitor. Furthermore the monitor will review

the TMF at the study site, study drug storage at the visits and check the drug accountability at the close-out visit.

During the interim monitoring visit, the monitor will review the study drug administration, treatment compliance, and the performance of assessments and to determine whether all Adverse Events are appropriately reported within the time periods required by GCP, the protocol, the sponsor, and the German requirements.

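### Section 18 tabulates skin and eye irritation only as frequencies per time point, which show net change and not how many patients got worse (minor)

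*Protocol*

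**What the plan says.** Sections 15.5.3 and 15.5.4 state the questions: "It will be investigated, whether the investigational products may cause symptoms of skin irritation" and "It will be investigated, whether the investigational products may irritate the eyes". Both variables use a four-category score. Section 15.5 places the pre-treatment scores ("baseline as well as assessments on day 7) will be performed within 1 hour before administration"), so each patient has a score shortly before each application and further scores after it.

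Section 18 lists the time points for skin, "Secondary infection, erythema, excoriation of the skin at -1h (baseline assessment), day 0 (0h, 1h), day 1, day 7 (pre-treatment, 0h, 1h) and day 10", and for eyes, "Irritation/Redness of the eyes at -1h (baseline assessment), day 0 (0h, 1h), day 1, day 7 (pre-treatment, 0h, 1h) and day 10 p.a". For each it then names the same summary: "Frequencies and percentages (related to number of patients with information) will be given for each symptom". Section 16.2 sets the layout: "categorically scaled variables: counts and percentages) by visit and treatment". No count of new or worsened patients and no shift table is named.

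The one stated patient-level use of a pre-treatment score is in footnote B of the flow chart: "on day 7 the pre-treatment assessment for irritations (skin, eyes) have to be used for decision about withdrawal due to severe irritation". Section 14.5 lists that finding among the withdrawal criteria.

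**The concern.** The question is about what happens to a patient after the product is applied. The named summary describes how many patients show a sign at each time point. The two differ when some patients improve while others get worse.

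Section 9 says that infestation causes intense itching, so scratch-related skin signs before treatment are plausible, and they may heal as the lice clear. Local irritation is also the harm that sections 13.1.2.1 and 13.1.2.2 describe for the products. A table of frequencies could therefore look flat or falling in an arm where a noticeable number of patients newly developed a sign.

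Two features of section 18 add to this. Percentages are taken among patients with data, so a patient withdrawn on day 7 for severe irritation may be missing from the later rows. And global tolerability is tabulated for each score but irritation for each symptom, so it is unclear whether a shift from mild to severe would show.

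Local tolerability is rated only after administration (section 15.5.2). The skin and eye scores are thus the graded tolerability data that allow a before-and-after comparison within the patient.

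**Working it through.** **Arm size.** Section 16.5 gives 42 evaluable patients (90% against 70%, two-sided 0.05, 90% power). Normal approximation: n = (1.960·√(0.7·0.3) + 1.282·√(0.9·0.1))² / 0.2² = 41.13, so 42. Inflation: 42 × 1.1 × 1.05 = 48.51, so 49, rounded to 50. The plan's figures reproduce, and 50 per arm is used below. The irritation analysis has no stated figure of its own.

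**Assumed inputs.** The protocol gives no pre-treatment prevalence (b), no share healing (r) and no graded rate of new irritation among patients clear before treatment (n). All three are assumptions.

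**Net change within an arm.** Frequency afterwards = b(1 − r) + (1 − b)n. The visible change is therefore (1 − b)n − b·r: new cases minus healed cases.

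| b | r | n | Before | After | Visible change | New cases |
|---|---|---|---|---|---|---|
| 20% | 80% | 20% | 10/50 | 2 + 8 = 10/50 | 0 points | 8/50 (16%) |
| 30% | 50% | 20% | 15/50 | 7.5 + 7 = 14.5/50 | −1 point | 7/50 (14%) |
| 40% | 30% | 15% | 20/50 | 14 + 4.5 = 18.5/50 | −3 points | 4.5/50 (9%) |
| 30% | 30% | 20% | 15/50 | 10.5 + 7 = 17.5/50 | +5 points | 7/50 (14%) |
| 20% | 0% | 20% | 10/50 | 10 + 8 = 18/50 | +16 points | 8/50 (16%) |

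The first three rows show masking. The fourth shows that the frequency can also rise despite healing. The last row is close to the 0h and 1h situation: the earlier score was taken within the hour before administration, r is near zero, and the rise equals the new cases.

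**Between arms.** Take b = 30% in both arms, with n = 15% against 5%. The true difference in new cases is 0.7 × (0.15 − 0.05) = 7 points.

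- Healing 80% in both: (0.06 + 0.105) − (0.06 + 0.035) = 7 points. Nothing is lost.
- Healing 90% against 70%: (0.03 + 0.105) − (0.09 + 0.035) = 1 point.
- Healing 90% against 60%: (0.03 + 0.105) − (0.12 + 0.035) = −2 points.

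The contrast is distorted only if healing differs by arm.

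**Denominators.** If k irritated patients are withdrawn on day 7 and give no later score, x/50 becomes (x − k)/(50 − k), which is lower whenever x < 50. With x = 10 and k = 1 (assumed), 20.0% becomes 9/49 = 18.4%. Section 14.5 asks for a post-study examination where possible, so this loss is possible but not certain.

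**The case against.** The other side is strong on several points.

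- **SAP content.** A reader might infer that frequencies are the only analysis that will ever be done. The protocol does not say so. Section 16.6 allows further tests and leaves details to an SAP that is not shown, and shift tables are commonly placed there. What stands is narrower: section 18 itself chooses a summary, and that summary does not answer the question in sections 15.5.3 and 15.5.4.
- **Visible baseline.** Pre-treatment frequencies appear in the same tables, by arm. A chance imbalance before treatment would be seen, and it can occur in any randomised safety table. It is not an error in the plan.
- **Adverse events.** Section 15.7.3.1 makes deterioration of a pre-treatment sign an adverse event, section 15.7.3.3 requires its documentation, and section 18 reports treatment-emergent events by frequency. This covers much of the gap. It depends on a separate entry, no rule ties a one-category change in score to that entry, and events are tabulated by preferred term and not by score.
- **Timing.** A reader might infer that irritation right after application is hidden. At 0h and 1h there is almost no time for healing, so it is not.
- **Eyes.** A reader might infer that infestation also confounds eye redness. Nothing in the protocol links lice to the eyes, so for eyes only the unused pairing of scores remains.
- **Rates.** Section 13.1.2.2 classes local skin irritation with the reference product as rare, at most 1/1000, or 50 × 0.001 = 0.05 patients per arm. The 5% to 20% assumed above is at least 50 times that. Leaflet reports are not solicited graded examinations and may understate what staff would score, but the illustrations show a mechanism and not an expected size.

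**Conclusion.** The point holds in a limited form. The summary named in section 18 gives net change per time point and cannot show how many patients newly developed or worsened a sign, although the paired scores are collected. For skin, healing can mask new cases on days 1, 7 and 10. Withdrawal on day 7 may also remove some of the worst cases from later rows, for skin or eyes.

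Under the assumed rates, up to 8 of 50 new cases can show as no change. This rests on substantial irritation before treatment, substantial healing, and rates of new irritation far above the leaflet figure. Distortion of the arm comparison also needs unequal healing.

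The documents do not support saying that the plan hides product irritation in general: the scores closest to exposure, the tabulated pre-treatment level and the adverse event route all work against that. Severity is low. This is a descriptive secondary safety analysis, and neither the primary nor the comparative efficacy conclusion is affected.

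**What to change.** In section 18 or the SAP, for each skin sign and for eye redness, add:

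1. Per arm, the number and percentage of safety-population patients whose score worsened by at least one category from the day 0 pre-treatment score to the worst score at any later assessment, including the day 7 pre-treatment score. Patients withdrawn on day 7 then stay in the count.
2. Separately, worsening at day 7 (0h, 1h) and day 10 from the day 7 pre-treatment score. This must not replace item 1. A patient scored 1 on days 0 and 1, then 3 before treatment on day 7 and 3 on day 10, has worsened by two categories from day 0 but shows no change from the day 7 reference.
3. The worse eye as the patient's eye score.
4. A shift table of pre-treatment against worst later score, and a descriptive 95% confidence interval for the arm difference.

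Keep the planned frequencies. The cost is a few lines of text and a few more safety tables. No new data or visits are needed, and no clinical rule changes.

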21.1 Independent Ethics Committee (IEC)

The documents required by the ICH-GCP regulation, the German Drug Law and Medical Device Law including study protocol, informed consent form as well as any subsequent amendment will be submitted to the relevant Independent Ethics Committee for positive vote.

21.2 Ethical conduct of the study

The study will be conducted in accordance with the study protocol, the ethical principles of the Declaration of Helsinki, ICH-GCP guidelines (International Conference on Harmonisation of Technical Requirements for registration of Pharmaceutical for Human Use – Good Clinical Practice), the requirements of the German Drug Law including the GCP regulation, and the German Medical Device Law.

21.3 Volunteer information and consent

The patient will receive a patient information document together with a consent form. The patient information document contains all relevant information about the study in accordance with the GCP requirements.

Every patient has to be informed verbally and also in writing by receiving the patient information document. The written information for patients must be approved by Ethics Committee. The consent form must be signed and dated by the patient prior to the start of the study. The informed consent form must be signed and dated by the physician who conducted the informed consent discussion. The patients must be given a copy of the document.

Every patient has the right to refuse further participation in the study at any time and without giving reasons.

According to the stipulations of the German Federal Data Protection Act, confidentiality and pseudonymity of the patients are assured.

Since minors will be enrolled in this trial, special requirements for this patient group are described in chapter 22.

22.1 Informed consent and assent

As the minor is unable to provide legally binding consent, the legal representative/s has/have to give informed consent on his/her behalf prior to enrolling a minor in the trial. In case both parents are the legal representatives it may be sufficient that at least one parent gives the informed consent, while a letter of attorney of the other parent must be available prior to informed consent process and signing.

The parent(s)/legal representative will be given sufficient time and necessary information to consider the benefits and risks of involving the minor in the clinical trial. Information will be given by experienced personnel to parent(s), or the legal representative on the purpose of the trial and its nature, the potential benefits and risks, and the name of investigators(s) who are responsible for conducting the trial with background professional information (such as education, work experience) and direct contact details (telephone, address, e-mail).

There will not be financial inducement to enrol the minor in the trial; no financial incentive will be offered (other than compensation of expenses and time spent).

Parent(s)/legal representative will be informed of the possibility to revoke informed consent even though it was made in writing, in line with Article 4(d) of the Clinical Trials Directive.

Parent(s)/legal representative will be reassured that the child's treatment will not be prejudiced by withdrawal from the trial, in line with Article 4(d) of the Clinical Trials Directive.

Consent will be obtained from the parent(s)/legal representative before assent is sought from the child, in line with Article 4 (a), (b) and (c) of the Clinical Trials Directive.

Parent(s)/legal representative will be made aware of the rights to refuse participation in a clinical trial and are entitled to withdraw informed consent, without giving reasons.

Parent(s)/legal representatives will be reassured that the withdrawal from the trial will not prejudice the child. Legal representatives who gave informed consent for a child to participate in clinical trials will have the opportunity to follow research as it proceeds (unless clinically inappropriate, e.g., during an operation under general anaesthesia), so as to be able to withdraw the child from the research at any time.

Minors will be involved in discussions and decision-making process only after obtaining consent from the parent(s) or the legal representative, as, where appropriate, the central role of parents should be recognised. An assent (age appropriate) in addition to informed consent of the legal representative is required. If the child's assent is not collected, this will be recorded in the consent form signed by the parents/legal representative and investigator, with the reasons.

Separate information sheets and consent and assent forms will be used in order to provide age appropriate information. Objections raised by a minor at any time during a trial will be considered. The child's will is respected any time, provided it is not considered detrimental to his/her health. The child will not be forced to provide reasons. The legal representative's consent should be checked. The child will be informed of the possibility to withdraw from the trial.

22.1.1 Infants and pre-school children

In this age group, it is not possible to obtain assent and the understanding of research is not expected.

Where the child has some capacity of understanding (pre-school children), age-appropriate information will be provided despite the fact that it will not be possible to obtain assent.

22.1.2 Children of school age (from about 6 years old)

In any case assent, preferably in writing will be obtained when the child is able to read and write, and keeping track of such assent will be performed.

22.1.3 Consent and assent in adolescents

Discretion and professional secrecy vis-à-vis parents when dealing with adolescents binding health professionals will be respected. The specific aspects of disclosure to parents of information concerning adolescents will therefore be taken into consideration for clinical trials in this age group, as well as emancipation status, and age to consent to medical care.

In addition to the requirement for the consent of parents or the legal representative, additional informed consent to participate in clinical trial is required for enrolment of minors of this age group.

When consent is sought from an adolescent who is also a parent of a child to be included in a trial, precautions will be taken to ensure that information provided is sufficiently understood.

